- ❖ **Primary Objective 1:** Evaluate the treatment patterns of insulin including observed total daily dose [TDD] in claims, adherence, prescription fill rate, claim gaps, persistence and concomitant medication use among T2DM patients before and after U-500R syringe initiation and U-500R Kwikpen initiation separately as well as before and after U-500R device switch from syringe to Kwikpen:
 - Characterize U-500R Kwikpen patients;
 - Determine differences between treatment patterns before and after U-500R Kwikpen initiation;
 - Determine differences between treatment patterns before and after U-500R syringe initiation; and
 - Determine differences between treatment patterns before and after U-500R device switch from syringe to Kwikpen.

Research Objective 2: Treatment Outcomes

- ❖ **Primary Objective 2:** Evaluate the HbA1c level among T2DM patients before and after U-500R syringe initiation and U-500R Kwikpen initiation separately, as well as before and after U-500R device switch from syringe to Kwikpen:
 - Determine differences between HbA1c level before and after U-500R Kwikpen initiation;
 - Determine differences between HbA1c level before and after U-500R syringe initiation;
 - Determine differences between HbA1c level before and after U-500R device switch from syringe to Kwikpen; and
 - Determine whether observed TDD in claims or insulin adherence played a role in HbA1c changes among U-500R syringe initiators, U-500R Kwikpen initiators, and device switchers from syringe to Kwikpen.
- ❖ **Secondary Objective 2a:** Evaluate the hypoglycemic events among T2DM patients before and after U-500R syringe initiation and U-500R Kwikpen initiation separately, as well as before and after U-500R device switch from syringe to Kwikpen:
 - Determine differences between hypoglycemia events before and after U-500R Kwikpen initiation;
 - Determine differences between hypoglycemia events before and after U-500R syringe initiation;

[2018-7241 Study Identifier] Observational Study Protocol

- Determine differences between hypoglycemia events before and after U-500R device switch from syringe to Kwikpen; and
 - Determine whether observed TDD in claims or insulin adherence played a role in hypoglycemic events among U-500R syringe initiators, U-500R Kwikpen initiators, and device switchers from syringe to Kwikpen.

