Claim gaps	Truven: Outpatient pharmacy claims table VHA: Pharmacy file	The average gap between prescription fills of insulins will be calculated in the pre- and post-index periods among all the study cohorts.
Concomitant medications ^{18,19,20}	Truven: Outpatient pharmacy claims table VHA: Pharmacy file	A flag will be created for patients prescribed antihyperglycemic agents (AHA): thiazolidinediones, sulfonylureas, biguanides, meglitinides, alpha-glucosidase inhibitors, DPP-4 inhibitors, bile acid sequestrants, fixed-dose combinations, GLP-1 receptor agonists, and amylin agonists (Appendix 1).

[2018-7241 Study Identifier] Observational Study Protocol

HbA1c ²¹	VHA: Lab file	The HbA1c value in the baseline and follow-up period for each index event will be reported. Baseline HbA1c (pre-index HbA1c) will be the HbA1c measurement -90/+30 days of the index date. For patients with multiple HbA1c measurements within this period, the measurement taken closest to the index event date will be reported as the baseline HbA1c value. The follow-up HbA1c value will be the HbA1c measurement taken furthest in the time period after the 30 day-post index event date. However, based on the sample size, HbA1c within 2 months prior to the end of the study follow-up will be considered as the post-index HbA1c.
Hypoglycemic events	Truven: Inpatient service table, outpatient service table VHA: Inpatient and outpatient files, Lab file and Pharmacy file	Hypoglycemia events in the pre-index and post-index period will be evaluated using the ICD-9 codes from the Ginde algorithm (Appendix 1) ²² or the presence of a cutoff of blood glucose ≤ 70 mg/dL, or any evidence of intramuscular glucagon administration (Appendix 1). Hypoglycemia event occurred on or after the index date will be considered as the follow-up hypoglycemia event; and hypoglycemia event occurred on or prior to - 1 day of the index date will be considered as the baseline hypoglycemia event. Number of hypoglycaemia events per patient per year (PPPY) will be reported in both the pre-index and post-index periods.
Prescribed TDD	Linked Truven claims and EMR data:	The prescribed physician TDD will be calculated, and will be reported both as continuous and categorical variable.

[2018-7241 Study Identifier] Observational Study Protocol

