6.4 Other Analyses**6.4.1 Outcomes Analyses**

All the analyses will be performed separately in VHA, linked Truven claims and EMR data, Truven claims database, and the pooled VHA and linked Truven claims and EMR data.

Pooling Multiple Databases

The VHA and linked Truven Claims with EMR databases will be pooled. To remove potential duplicate patient records from multiple data sources, probabilistic matching will be utilized. Potential duplicate patients across the databases will be identified by a STATinMED Research algorithm using age, sex, hospital admission date, hospital discharge date, and primary discharge diagnosis.^{23,24} Identified patients with the same information for the variables listed above will be assumed to be the potential duplicated patient and flagged in the pooled dataset. The rate of duplicate patients is expected to be low based on references and a previous study (<1%).²³ Duplicate patients can be potentially retained in the analytic file if the rate is low. After pooling, we will check if there are any potential duplicates across datasets. If the % will be small (<3%), we will not delete any duplicates because the impact to the final outcomes are considered minimal. If the % is significant (>3%), we will remove the duplicated records from the dataset that has the

[2018-7241 Study Identifier] Observational Study Protocol

larger sample size. Analyses will be conducted on each individual database as well as the pooled dataset.

Research Objective 1: Primary Objective 1Descriptive Analysis

All study variables including demographics, clinical characteristics, and treatment patterns of insulin (i.e., TDD, adherence, prescription fill rate, claim gaps, persistence, and concomitant medication use) will be analyzed descriptively before and after U-500R syringe initiation and U-500R Kwikpen initiation, and before and after U-500R device switch from syringe to Kwikpen.

Numbers and percentages will be provided for dichotomous and polychotomous variables. Means and standard deviations (SDs) will be provided for continuous variables. McNemar's test will be used to determine statistical significance of before and after values for categorical variables, and the paired t-test will be used to assess the statistical significance of before and after values in continuous variables.

Multivariate Analysis

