Mixed linear model will be used to evaluate factors associated with HbA1c level in the pre- and post-index periods among U-500R syringe initiators, U-500R Kwikpen initiators, and U-500R device switchers. Mixed linear model is used for studies with a longitudinal feature in which a continuous outcome variable is measured for the same subject repeatedly over the time period. Based on the distribution of the data, observations measured for the same subject are likely to be correlated over the study period and these data are considered as "multilevel" data. In addition, mixed linear model has a mixed effect consisting both fixed and random effects. For this objective, mixed linear model helps to evaluate the effect of both time varying and time-independent variables on the HbA1c, while taking into account for correlation due to multiple assessments from the same individual. In the current model, HbA1c level which is measured at two time intervals (before and after the index event; U-500R initiation/device switch), will be considered the dependent variable. Observed TDD will be considered as the time varying covariate in the model (measured both before and after the index event), and the time independent covariates include the demographic and clinical characteristics.

The complete list of covariates will include:

- age
- sex
- race
- BMI
- baseline CCI score
- observed TDD from claims
- time (pre/post)

Note: Age, sex, race, BMI, and CCI score will be assessed during pre-index period. Observed TDD will be calculated during the entire pre-index and post-index periods, respectively. Pre-index

[2018-7241 Study Identifier] Observational Study Protocol

HbA1c will be defined as the HbA1c measurement -90/+30 days of the index date. For patients with multiple HbA1c measurements within this period, the measurement taken closest to the index event date will be reported as the pre-index HbA1c value. Post-index HbA1c will be defined as the HbA1c within 2 months of the end of the follow-up period.

Adherence will not be included as one of the covariates here due to the high collinearity between time and adherence. Hence, further mediation analysis will be performed to determine the mediator effect of adherence on HbA1c.

Mediation Analysis:

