Mediation analysis following the Baron and Kenny's steps will be considered to understand the impact of index event (time: pre-index indicates use of othe insulin and post-index indicates U-500R use) on HbA1c through potential mediators. Adherence is considered as a potential mediator between the HbA1c and time. The key steps in mediation analysis include a model of the mediator (adherence) as a function of the predictor (time) and a model of the outcome (HbA1c) as a function of both the mediator (adherence) and the predictor (time). Bootstrapping method will be used to test the effect of mediator. The detailed steps are described below:

Step 1: Effect of predictor (time) on the outcome (HbA1c):

In the first step, the effect of time on the dependent variable HbA1c will be assessed. Statistically, a significant relationship between the two variables will trigger the next step of the mediation analysis. However, it is suggested that the clinical significance and theoretical evidence should be considered in the case of failure to detect an association that is statistically significant. Since the effect of time on HbA1c is the primary interest of this analysis, we will carry out the next step regardless of the significance between time and HbA1c.

Step 2: Effect of predictor (time) on the mediator (adherence):

The effect of time (predictor) on the hypothesized mediator adherence will be assessed, and adherence will be considered as a dependent variable in the model. Potential mediation effect will be supported by a statistically significant relationship between time and adherence, which will lead to the next step of the analysis.

Step 3: Combined effect of predictor (time) and mediator (adherence) on the outcome (HbA1c):

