Zero-inflated negative binomial mixed model will be used to evaluate factors associated with number of hypoglycemia events PPPY in the pre- and post-index periods among U-500R syringe initiators, U-500R Kwikpen initiators, and U-500R device switchers. Zero-inflated negative binomial distribution is a mixture of a binary distribution that is degenerate at zero and an ordinary count distribution such as negative binomial. In cases of outcome variable being repeatedly measured from the individual subjects, zero inflated models are extended to include random effects to account for the correlation among the repeated measures within a subject. In the current model, the number of hypoglycemia events which might have more zeroes (for example not every patient might have a lab visit for glucose) and is measured at two time intervals (before and after the index event; U-500R initiation/device switch), will be considered the dependent variable. Observed TDD, and HbA1c will be considered as the time varying covariates in the model (measured both in the before and after index date), and the time-independent covariates will include the demographic and clinical characteristics.

The complete list of covariates will include:

- age
- sex
- race
- BMI
- baseline CCI score

[2018-7241 Study Identifier] Observational Study Protocol

- observed TDD from claims
- HbA1c
- time (pre/post)

Note: Age, sex, race, BMI, and CCI score will be assessed during pre-index period. Observed TDD and HbA1c will be calculated during the entire pre-index and post-index periods, respectively. Pre-index HbA1c will be defined as the HbA1c measurement -90/+30 days of the index date. For patients with multiple HbA1c measurements within this period, the measurement taken closest to the index event date will be reported as the pre-index HbA1c value. Post-index HbA1c will be defined as the HbA1c within 2 months of the end of the follow-up period.

Research Objective 2: Secondary Objective 2bDescriptive Analysis

Treatment outcomes (HbA1c and number of hypoglycemic events) and prescriber behavior (observed TDD in claims and prescribed TDD from the physician) will be analyzed descriptively and quarterly before and after U-500R syringe initiation and U-500R Kwikpen initiation, and before and after U-500R device switch from syringe to Kwikpen.

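### The HbA1c and hypoglycemia models leave out concomitant antihyperglycemic use, so a net change in those drugs at index cannot be separated from the effect of U-500R initiation or the device switch

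*Protocol*

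**What the plan says.** Table 3 (section 5.5) defines concomitant medication from pharmacy claims: "A flag will be created for patients prescribed antihyperglycemic agents (AHA"), followed by ten drug groups that include sulfonylureas, meglitinides and GLP-1 receptor agonists. Primary Objective 1 (section 4.1) covers "prescription fill rate, claim gaps, persistence and concomitant medication use among T2DM patients before and after U-500R syringe initiation", and continues to Kwikpen initiation and the device switch. Section 6.4.1 handles this by description: "persistence, and concomitant medication use) will be analyzed descriptively before and after U-500R syringe initiation", with McNemar's test for categorical variables.

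The HbA1c model (section 6.4.1, Primary Objective 2) is introduced with "The complete list of covariates will include". The list is age, sex, race, BMI, baseline CCI score, observed TDD and time. The first five are assessed in the pre-index period only. On the covariate that may change between periods, the protocol says "Observed TDD will be considered as the time varying covariate in the model (measured both before and after the index event"). The hypoglycemia model (Secondary Objective 2a) has the same list plus HbA1c: "Observed TDD, and HbA1c will be considered as the time varying covariates in the model".

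The mediation text that follows the HbA1c model explains how the time term is to be read: "time: pre-index indicates use of othe insulin and post-index indicates U-500R use". It also gives that term its weight: "Since the effect of time on HbA1c is the primary interest of this analysis".

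**The concern.** Each patient is compared with himself or herself. Characteristics fixed at baseline have the same value in both periods, so entering them as main effects cannot remove confounding by something that changes at index. Only time-varying terms can do that. The HbA1c model has one such term, insulin dose, and the hypoglycemia model has two.

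Non-insulin glucose-lowering drugs act on both outcomes and can be started or stopped around the same time as U-500R. If their use shifts, the time coefficient carries that shift together with whatever U-500R or the Kwikpen did. A net start of such drugs could make an HbA1c improvement look larger. A net withdrawal could hide one, or could lower hypoglycemia counts and mask a rise. A reader of the results would have no adjusted estimate with which to tell these apart.

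**Working it through.** **Step 1. Compare the covariate lists with the variables collected.** The plan states no figure to reproduce: section 6.1 gives database counts and no power calculation, and nothing is assumed about drug changes.

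| Item | HbA1c model | Hypoglycemia model |
|---|---|---|
| Fixed at baseline | age, sex, race, BMI, CCI | age, sex, race, BMI, CCI |
| Time-varying, besides time | observed TDD | observed TDD, HbA1c |
| Antihyperglycemic use | absent | absent |

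**Step 2. Look for a repair elsewhere.** The note under Primary Objective 3 makes the listed covariates depend on availability in each database; it does not add any. No sensitivity analysis, restriction to stable background therapy, or exclusion for drug changes is stated. For device switchers, Table 3 counts only U-500R units in TDD, so changes in their other insulin are unadjusted as well.

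**Step 3. Write down what the omission does.** For the linear HbA1c model, take the within-patient difference:

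change in HbA1c = τ + γ × (change in TDD) + β × (change in drug use) + error.

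If drug use is left out and its change is unrelated to the change in TDD, the time coefficient estimates τ + β × (post-index share using the drug − pre-index share). If the two changes are related, part of the drug effect moves into the TDD coefficient instead.

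**Step 4. Illustrate the size.** All inputs here are assumed; none comes from the documents.

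- Net rise of 5 points, effect −0.5: 0.05 × (−0.5) = −0.025 point
- Net rise of 10 points, effect −0.5: 0.10 × (−0.5) = −0.05
- Net rise of 10 points, effect −1.0: 0.10 × (−1.0) = −0.10
- Net rise of 20 points, effect −1.0: 0.20 × (−1.0) = −0.20

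The signs reverse for a net withdrawal.

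**Step 5. Ask how often such a shift would pass for a finding.** With a true effect of zero, SE = SD/√n, and the chance of two-sided p<0.05 is Φ(d/SE − 1.96) + Φ(−d/SE − 1.96). The SD of the paired change is assumed to be 1.5 to 2.0. The n of 4,066 is the Table 4 VHA Kwikpen count with at least two HbA1c values; it precedes most selection criteria and is therefore a ceiling. The n of 1,000 is assumed.

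| n | SE (SD 1.5; 2.0) | shift 0.05 | shift 0.10 |
|---|---|---|---|
| 1,000 | 0.047; 0.063 | 0.18; 0.12 | 0.56; 0.35 |
| 4,066 | 0.024; 0.031 | 0.57; 0.36 | 0.99; 0.89 |

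For example, 0.10/0.0474 = 2.11, and Φ(2.11 − 1.96) = 0.56.

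**Step 6. Check by simulation.** The set-up was a true time effect of zero, drug use rising from 20% to 30%, a drug effect of −1.0, n = 1,000 and 30 runs of a random-intercept model. With time and TDD only, the mean time coefficient was −0.10. With a time-varying drug term added, it was −0.01. The mean agrees with step 4; 30 runs are too few to judge error rates.

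No corresponding figure is offered for the zero-inflated hypoglycemia model. HbA1c may absorb part of a drug's effect there, but not a direct effect on hypoglycemia.

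**The case against.** The strongest reply concerns the estimand. Table 3 lists concomitant medication among the outcomes, and Objective 1 treats it as a treatment pattern that the index event may alter. If a drug was added or stopped because U-500R was started, adjusting for it conditions on a consequence of the exposure. The unadjusted time term then estimates the total pre/post change, which is a legitimate answer to the objective of determining differences before and after.

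This stands as a reason not to replace the planned model. It does not argue against a second version. The plan already adjusts for a treatment variable measured after index, observed TDD, so its time term is not a pure total change either. The mediation text also reads time as U-500R against other insulin, which goes further than a bare pre/post difference.

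A second reply is that the descriptive comparison will show any large shift in drug use. That is true and useful, but it does not adjust the coefficient.

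Three stronger readings may tempt a reader and are not supported:

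- That drug changes will be credited to U-500R as benefit. The documents do not show that net changes occur, or in which direction.
- That the mediation results inherit the same adjusted coefficient. The mediation steps describe models in time and adherence and name no other covariates, so this is not stated.
- That ready-made flags cover every class. Table 3 speaks of a flag and names ten groups, SGLT2 inhibitors not among them; the Appendix 1 content is not visible. The entry gives no time window.

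**Conclusion.** The omission is confirmed in the text and is not repaired elsewhere. Because the protocol presents the HbA1c and hypoglycemia covariate lists as complete, it is a choice the protocol fixes, not a detail left for an analysis plan. The consequence is that a net change in other glucose-lowering drugs cannot be separated from U-500R initiation or, for switchers, from the change of device.

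Direction and size are unknown. The illustrative 0.025 to 0.20 HbA1c point rests on assumed shifts in drug use and assumed drug effects. The probabilities of significance also rest on an assumed SD and on sample sizes that are assumed or are upper limits. A large sample does not reduce such a bias; it makes a small one more likely to reach significance. Adjusting for these drugs would not turn an uncontrolled pre/post comparison into a causal one, but it would address one collected factor. The change is worth making.

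**What to change.** Keep the planned HbA1c and hypoglycemia models. For each, prespecify a second version with time-varying pre/post flags for the antihyperglycemic classes named in Table 3: at least GLP-1 receptor agonist, sulfonylurea or meglitinide, and any other.

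Define each flag's window so that use precedes the outcome it explains. This needs care because the baseline HbA1c may be taken up to 30 days after index, and because a drug first filled after the follow-up HbA1c cannot explain it.

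Report the time coefficient without the flags, with the flags, and in patients whose classes did not change. State that the version without flags describes the total pre/post change in this respect, and that the version with flags describes the change at fixed background therapy, because some drug changes may follow from starting U-500R.

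The cost is building time-aligned flags from pharmacy claims already in hand and reporting additional model results for each cohort and database. No new data are needed.

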5.1 Summary of Research Design

This will be a retrospective cohort study using the Veterans Health Administration (VHA) database, linked Truven MarketScan Claims and Electronic Medical Records [EMR] Data (LCED), as well as the Truven MarketScan claims databases (Table 1).

Multiple datasets will be used due to unavailability of the certain study outcomes in one single dataset. (e.g. out-of-pocket costs are not available in VHA dataset; HbA1c not available in Truven claims dataset). Additionally, using multiple datasets will improve the generalizability of the study, and since U-500R Kwikpen is recently available in the market, linking two databases would ensure that the study has adequate sample size. Furthermore, the patient population in the VHA primarily consists of veterans across the country (non-commercial database), whereas Truven is an employment-based health insurance (commercial database). Therefore, conducting the analysis separately in each of these databases as well as in the pooled dataset would give a more comprehensive and complete picture of the treatment patterns and outcomes in the real-world in this patient population.

To meet the analytical requirement of multiple research objectives, the following criteria will be used:

- The first prescription claim date for U-500R syringe or U-500R Kwikpen administration will be considered U-500R initiation and designated as Index Event 1 (syringe: Index Event 1a; Kwikpen: Index Event 1b).
- The date for U-500R device switch from syringe to Kwikpen will be designated as Index Event 2.
- The study period will range from 01APR2013-31MAR2018 for VHA and LCED; and 01JUL2013-30JUN2018 for Truven MarketScan claims.
- The identification period will be 01JAN2014-30JUN2017 for VHA and LCED; and 01APR2014-30SEP2017 for Truven MarketScan claims; the baseline and follow-up periods will be 9 months pre- and 9 months post-index date, respectively (Figures 1-3).

[2018-7241 Study Identifier] Observational Study Protocol**Table 1 Study Design by Objectives**

Research Objectives	Database (study period)	Study Cohorts
Research Objective 1		
Primary Objective 1	
 • VHA (01APR2013-31MAR2018) • Pooled VHA and LCED (01APR2013-31MAR2018) • Truven MarketScan Claims Database (01JUL2013-30JUN2018) 	U-500R syringe initiators U-500R Kwikpen initiators U-500R device switchers
Research Objective 2		

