Individual Comorbidities ¹⁷	Truven: Inpatient service table, outpatient service table VHA: Inpatient and outpatient files	A flag will be created using ICD-9/10-CM codes (Appendix 1) for patients diagnosed in the baseline period with any of the following individual comorbidities: retinopathy, nephropathy, neuropathy, coronary artery disease, peripheral vascular disease, congestive heart failure, hypertension, depression, obesity, or malignant tumor.
Health Economics Outcomes Research (HEOR) Outcomes		
Observed TDD in claims	Truven: Outpatient pharmacy claims table VHA: Pharmacy file	
The observed insulin TDD will be calculated as the total number of insulin units/total unique days of supply as recorded in claims and will be calculated both in the pre-and post-index periods among the U-500R syringe initiators, U-500R Kwikpen initiators, and the U-500R device switchers. TDD will be reported both as continuous and categorical variable.
 
For U-500R syringe initiators (index event 1a): Total insulin units correspond to all the insulin units in pre-index and post-index periods respectively Additionally the TDD of U-500R syringe only will be reported in the post-index period
 
For U-500R Kwikpen initiators (index event 1b): Total insulin units correspond to all the insulin units in pre-index and post-index periods respectively Additionally the TDD of U-500R Kwikpen only will be reported in the post-index period
 
For U-500R device switchers (index event 2): For device switchers the total insulin units correspond only to the total units of U-500R syringe use in the pre-index period and U-500R Kwikpen in the post-index period
 
Note:

[2018-7241 Study Identifier] Observational Study Protocol

		For the unique days supply in patients with evidence of a basal-bolus regimen, or basal/bolus-pre-mixed or basal/bolus-U-500R the overlap days will be adjusted for the concomitant use of basal and bolus insulins, but will not be adjusted within basal and within bolus insulins.

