Observed average daily dose (ADD) in claims	Truven: Outpatient pharmacy claims table VHA: Pharmacy file	
The observed insulin ADD will be calculated both in the pre-and post-index periods among the U-500R syringe initiators, U-500 Kwikpen initiators, and the U-500R device switchers. ADD will be reported both as continuous and categorical variable.
 
Pre-index ADD: total number of insulin units/ the total number of days in the pre-index period.
 
Post-index ADD: total number of insulin units/ the total number of days in the post-index period.
 
Additionally the ADD of U-500R syringe only and the U-500R Kwikpen only will be reported in the U-500R syringe initiators and Kwikpen initiators respectively.
 
Note: Total insulin units calculation in based on the similar approach as described in TDD.

Adherence	Truven: Outpatient pharmacy claims table VHA: Pharmacy file	
Adherence to insulin will be assessed using the proportion of days covered (PDC), and reported in categories of 0-20%, 20-40%, 40-60%, 60-80%, and 80%-100%. PDC will be calculated both in the pre-and post-index periods among the U-500R syringe initiators, U-500 Kwikpen initiators ,and the U-500R device switchers.
 
For U-500R syringe initiators (index event 1a):

[2018-7241 Study Identifier] Observational Study Protocol

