6.3 Significance Levels

Two-sided hypothesis testing will be applied to test the statistical significance, and multiple testing adjustment for controlling error rates will not be applied. A p-value of <0.05 will be considered statistically significant. SAS for Windows Version 9.4 will be used for all statistical analyses.

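### The stated reason for leaving adherence out of the HbA1c and cost models is unsupported and conflicts with mediation Step 3, and no model is clearly stated to hold time, dose and adherence together

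*Protocol*

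**What the plan says.** Primary Objective 2 (Protocol section 4.1) includes the aim "Determine whether observed TDD in claims or insulin adherence played a role in HbA1c changes". Primary Objective 3 asks how observed TDD and adherence relate to out-of-pocket and to total costs.

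Section 6.4.1 specifies a mixed model for HbA1c: "HbA1c level which is measured at two time intervals (before and after the index event; U-500R initiation/device switch), will be considered the dependent variable". Its covariates are age, sex, race, BMI, comorbidity score, observed TDD and time. The cost model has a similar list, again with TDD and time. After both lists the protocol states: "Adherence will not be included as one of the covariates here due to the high collinearity between time and adherence". Adherence then goes to a mediation analysis with time as predictor. Step 2 regresses adherence on time, and a significant result leads to Step 3. Step 3 adds adherence to the model relating time to the outcome.

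Table 3 defines adherence as "proportion of days covered (PDC), and reported in categories of 0-20%, 20-40%, 40-60%, 60-80%, and 80%-100" per cent, and observed TDD as "total number of insulin units/total unique days of supply as recorded in claims".

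**The concern.** The reason given is a numerical claim about the data, but no number accompanies it. It also rules out the very combination that Step 3 fits. If the collinearity really were high, Step 3 would suffer most: it reads a time effect that loses significance after adjustment as full mediation, and variance inflation alone could produce that. If the collinearity is not high, the reason for the exclusion falls away. The text needs correcting in either case.

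At stake is the answer to the dose-and-adherence part of two primary objectives. The listed outcome models hold dose without adherence. The opening description of the mediation models names adherence and time but not dose. Step 1 is expressly carried forward whatever its p-value, but Step 2 has no such waiver. If mean PDC does not change significantly, adherence may therefore never enter an outcome model, even though it could still vary between patients and relate to HbA1c or cost.

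**Working it through.** **Inputs from the protocol.** There are two periods per patient: "the baseline and follow-up periods will be 9 months pre- and 9 months post-index date, respectively" (section 5.1). Time is therefore a balanced binary indicator. PDC lies between 0 and 1. No PDC mean, SD or correlation is given, nor any effect size, so every such value below is an assumption. There is no stated figure to reproduce.

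**Step 1: collinearity of time and PDC.** Let m be the mean PDC change and s the SD of change.

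- Within patients: r² = m²/(m² + s²), so VIF = 1/(1 − r²) = 1 + (m/s)².
- Pooled over all observations, with d = m / SD of PDC: r² = d²/(d² + 4), so VIF = 1 + d²/4.

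Within-patient VIF at s = 0.25:

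- m = 0.05: 1 + 0.2² = 1.04
- m = 0.10: 1 + 0.4² = 1.16
- m = 0.20: 1 + 0.8² = 1.64
- VIF 5 needs m = 2s = 0.50

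At s = 0.15, VIF 5 needs m = 0.30.

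Over a wider range I took shifts of 0.05 to 0.20, PDC SD of 0.15 to 0.30 and pre/post correlation ρ of 0 to 0.7, with s = SD × √(2(1 − ρ)). The pooled VIF is 1.01 to 1.44. The within-patient VIF is 1.01 to 3.96, and at most 2.67 once the SD is 0.20 or more. A pooled VIF of 5 needs d = 4; at SD 0.25 that is a shift of 1.0, the whole PDC scale. A within-patient VIF of 5 or more appears only with a large and fairly uniform change, for example a shift of 0.30 with SD 0.15 and ρ of at least 0.5, or many of the combinations with a shift of 0.50.

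**Step 2: effect on the dose coefficient.** By Table 3, TDD is units over unique days of supply, PDC is covered days over period days, and average daily dose (ADD) is units over period days. So TDD × PDC is roughly ADD. Dose and adherence share the days-supply field, but the identity does not fix the sign of their correlation.

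I used simulated random-intercept models: 1,500 patients, two periods, 20 replicates per cell, PDC shift 0.10 and SD 0.25 before truncation to 0–1. The mean dose coefficient without PDC was:

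| TDD–PDC correlation | true dose −0.10, PDC −1.0 | true dose +0.10, PDC −1.0 | true dose +0.10, PDC +0.5 |
|---|---|---|---|
| −0.4 | 0.00 | 0.189 | 0.048 |
| −0.2 | −0.055 | 0.147 | 0.074 |
| 0 | −0.10 | 0.103 | 0.094 |
| +0.2 | −0.149 | 0.059 | 0.116 |
| +0.4 | −0.195 | −0.005 | 0.141 |

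With PDC in the model, the coefficient was within about 0.01 of its true value in every cell. Adding PDC barely changed the standard error of time: 0.039–0.040 without it, 0.039–0.043 with it.

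**Step 3: which stated model holds all three.** The HbA1c and cost models hold time and TDD without PDC. The opening text of each mediation section describes an outcome model in adherence and time, with no mention of TDD. The wording of Step 3 could mean the full listed model plus adherence, but does not say so. The adherence model under Primary Objective 1 holds time and TDD with PDC as outcome, so it describes the dose–adherence link but not HbA1c or cost.

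**The case against.** Leaving a hypothesised mediator out of the total-effect model for time is standard, whatever reason is written down. That stands, and the fix keeps that model. Nor is adherence dropped from the analysis: it is moved to the mediation steps.

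High collinearity is not impossible. The follow-up period opens with an index fill, while the baseline period requires only one qualifying claim, which could push PDC upward. That stands too: the claim is unlikely under ordinary PDC spread and not shown, rather than impossible. The protocol does not say whether data were examined before the sentence was written.

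Step 3 may be meant to carry TDD and the other covariates, and a SAP could say so. This reading is open, and is why the point is that no model is *clearly* stated to hold all three. A SAP would not remove the conflict between the stated reason and Step 3.

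If adherence lies downstream of dose, the coefficient without PDC is the total dose association, and adding PDC changes the quantity estimated rather than removing a bias. Errors in days of supply also enter both variables, and joint modelling does not cure that. Both stand, so the adjusted coefficient belongs beside the unadjusted one and not in its place.

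A reader might infer that omitting adherence attenuates the dose coefficient. The protocol does not support this. Attenuation with a protective dose and adherence effect needs a negative TDD–PDC correlation, which is nowhere established; other signs leave the coefficient unchanged, exaggerate it or reverse it.

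**Conclusion.** The point holds as stated in the heading. The collinearity reason has no figure behind it, is unlikely (within-patient VIF 1.04 to 1.64 for shifts of 0.05 to 0.20 at an assumed SD of change of 0.25), and conflicts with Step 3. The listed TDD coefficient is not adjusted for adherence and may differ from the adjusted one in either direction. In the simulated cells the difference ran from nil to about 0.10 on a true coefficient of 0.10 in absolute size, but those effect sizes and correlations are assumptions, so the table shows direction and sensitivity and does not predict this study's result. The dose-and-adherence questions in Primary Objectives 2 and 3 lack a clearly specified joint model that is certain to be fitted. This should be corrected; it does not undermine the pre/post comparison itself.

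**What to change.** In section 6.4.1, under both Primary Objective 2 and Primary Objective 3:

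- Delete the collinearity sentence. If PDC stays out of the total-effect model for time, give the reason that it is a hypothesised mediator.
- Add, for each outcome, one model with time, observed TDD, PDC and the covariates already listed, fitted regardless of the Step 2 result and with the VIF reported.
- Report the dose coefficient from both versions, labelled as total (without PDC) and net of adherence (with PDC).
- State that Step 3 carries TDD and the same covariates.

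The cost is one extra model per outcome, built from variables already derived. The time and dose coefficients in the added model are both net of adherence, so the two versions must be labelled clearly to avoid being read as rival estimates of the same quantity.
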